## 8.0 STUDY CALENDAR

Month	PreRx	1	2	3	4	5	6
MD Evaluation a	X						X
Laboratory Evaluation e	X						
Toxicity Evaluation b		X	X	X	X	X	X
Pregnancy test c	X						
colonoscopy and colorectal biopsies	X						X
Celecoxib Administration		X	X	X	X	X	X
Plasma for drug assay d	X		X		X		X

aMD will perform history and physical examination. Study subjects are specifically asked regarding CV events.

b Toxicity evaluation will be in person at the end of the study and by telephone 72 hours after initial intake then every 2 weeks for 6 months.

c Serum pregnancy test is performed in women who have childbearing potential.

d Plasma assay will be performed as in section 7.10.0.

e Laboratory evaluation are : fasting blood glucose, lipid profile, CBC, creatinine, bilirubin, and ALT

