### **7.2. 0 Pretreatment Evaluation**

**7.2.1** Pretreatment history (including medication history especially NSAID use) and physical examination will be performed. Physical examination should include heart, lung, and extremity examination. Study subjects are specifically asked regarding cardiovascular events (myocardial infarction, angina, stroke, arrhythmia or congestive heart failure) and cardiac symptoms (chest pain, palpitation, dyspnea, or edema).

**7.2.2** Laboratory evaluation: fasting blood glucose and lipid profile (cholesterol, LDL, HDL and triglyceride). CBC, creatinine, bilirubin, and ALT.

**7.2.3** Serum pregnancy test for women of childbearing age.

**7.2.4** Pretreatment history, physical, and laboratory data are acceptable within 35 days prior to start of protocol therapy (celecoxib).

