#### **7.8.0 Follow-up procedure**

Patients will be contacted by phone 72 hours after the first celecoxib doses and every 2 weeks (+/- three days) thereafter for toxicity assessment for the entire period of the study (6 months). Subjects will be asked to maintain a treatment diary (Appendix L) of celecoxib intake. Study subjects are specifically asked regarding cardiovascular events (myocardial infarction, angina, stroke, arrhythmia or congestive heart failure) and cardiac symptoms (chest pain, palpitation, dyspnea, or edema). Serum celecoxib levels will be done at the end of months 2, 4, and 6 (+/- seven days) of celecoxib treatment.

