### 9.2.0 Adverse Event Severity grading

Adverse event toxicity will be graded according to the defined NCI Toxicity scales (Appendix C) and appropriate action taken. Adverse events not included in the defined NCI toxicity criteria will be graded according to their effects on the daily activity of the study subjects:

- Grade 1: No limitation of daily activity
- Grade 2: Some limitation of daily activity
- Grade 3: Severe limitation of daily activity

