#### **9.4.0 Potential Expected Adverse events**

The biopsies required for the study are not expected to appreciably increase the small risk of serious adverse events that might otherwise happen during or after rectal endoscopic procedures. These potential risks can include bleeding and bowel perforation. The risk of perforation is expected to be lower in the rectal region than to what expected with higher colonic biopsies.

Possible side-effects with celecoxib can include: diarrhea, indigestion, headache; nasal congestion, sore throat, rhinorrhea and/or upper respiratory tract infection; abdominal pain, stomach pain, peptic ulcer disease, gastrointestinal bleeding, gas, nausea, back pain; extremity edema, dizziness, insomnia, tinnitus, liver function test abnormalities, hepatitis, jaundice, and/or rash. Celecoxib at a dose of 800 mg daily was found to increase risk of major fatal and non-fatal cardiovascular events by 3.4-fold compared to subjects who were taking placebo in the Adenoma Prevention with Celecoxib (APC) trial (<http://www.fda.gov/cder/drug/infopage/celebrex/celebrex-hcp.htm>). One incident of rhabdomyolysis has been reported in a patient taking celecoxib. The possibility of celecoxib being the cause of this incident cannot be excluded.

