#### **9.5.0 Measures to monitor side effects and manage adverse events**

Subjects will be observed for at least 60 minutes after biopsy procedures. Contact telephone numbers will be provided to ensure that medical staff may be easily reached. Subjects are asked to call in case of excessive bleeding or abdominal pain after the procedure. If excessive bleeding is evident after the procedure, the lesions will be cauterized. Surgical backup is available at all times.

Study subjects will be contacted by phone 72 hr after the first celecoxib doses and every 2 weeks thereafter for the rest of the celecoxib treatment duration for toxicity assessment. In addition, subjects will undergo a history and physical to assess for toxicity during a clinical visit at the end of the treatment. All adverse events will be followed according to good medical practices. "Unacceptable toxicity for a chemoprevention agent is defined as any Grade 3 or higher toxicity (NCI Common Toxicity Scale) for any of the listed categories or Grade 2 or higher allergic reaction or cardiac toxicity." If a study investigator determines that an unacceptable toxicity [Grade 3 or higher toxicity for any of the NCI Common Toxicity Scale categories or Grade 2 or higher allergic reaction or cardiac toxicity] is possibly related to celecoxib, then celecoxib will be stopped and the study Chair be informed. The PI will meet with Drs. [name] (study co-investigators) and [name] (study biostatistician) to perform a cumulative review of all adverse events and premature terminations every 6 months after study initiation or after completion of 15% of subject enrollment (enrollment of 6 patients). If any cardiovascular adverse event is identified for a follow-up period, [name], the study collaborating cardiologist, will participate in the review of the cumulative toxicity. The patient will be followed up according to good medical practices. As a part of the follow-up in case of unacceptable toxicity development, a telephone contact will be made at 30  $\pm$  7 days after celecoxib discontinuation to assess the resolution of the adverse event(s).

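### The stop rule for grade 3 or higher toxicity covers laboratory-defined toxicity, but the schedule has no safety laboratory panel after treatment starts, so symptomless cases have no scheduled route to the rule

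*Combined protocol and SAP*

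**What the plan says.** Section 9.5.0 defines unacceptable toxicity as "any Grade 3 or higher toxicity (NCI Common Toxicity Scale) for any of the listed categories", with a lower threshold (grade 2) for allergic and cardiac events. If an investigator determines that such a toxicity "is possibly related to celecoxib, then celecoxib will be stopped and the study Chair be informed". Section 9.2.0 takes the grading from the NCI scales in Appendix C.

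Section 9.4.0 lists the possible effects of celecoxib. They include "liver function test abnormalities, hepatitis, jaundice, and/or rash".

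The calendar in section 8.0 has a laboratory row, explained by the footnote "Laboratory evaluation are : fasting blood glucose, lipid profile, CBC, creatinine, bilirubin, and ALT". The row carries a mark in the pretreatment column and in no other. Section 7.2 places the same tests in the pretreatment evaluation: "Pretreatment history, physical, and laboratory data are acceptable within 35 days prior to start of protocol therapy".

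During treatment, toxicity is assessed by telephone at 72 hours and then every 2 weeks (7.8.0, 9.5.0), and in person at month 6 by history and physical examination (7.9.0). Blood is also taken during treatment: "Serum celecoxib levels will be done at the end of months 2, 4, and 6". Section 7.10.0 gives celecoxib level as the purpose of those samples.

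**The concern.** The stop rule is written to cover every category of the toxicity scale, and the protocol itself names a laboratory finding among the effects to expect. A liver function test abnormality without symptoms is seen only if someone measures it. The same holds for a silent rise in creatinine or fall in blood counts, which section 9.4.0 does not list but which the baseline panel measures.

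The protocol treats these values as relevant to safety, because section 5.1.2 sets entry limits for neutrophils, platelets, creatinine, bilirubin and ALT. Section 9.1.0 counts a condition that worsens on the drug as an adverse event, and worsening of a laboratory value cannot be shown without a second measurement.

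Two things are at stake. A patient with silent laboratory toxicity could stay on celecoxib for 6 months without the rule being considered. And the cumulative review in 9.5.0, like the compliance monitoring in 9.5.1, could report little or no laboratory toxicity because little or none was looked for. A reader of those reports might take that as reassurance.

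**Working it through.** The plan states no figure on this point, so the check sets the sections side by side.

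1. **What the rule needs.** A grade for any toxicity category (9.5.0). For a laboratory category that means an on-treatment value. Appendix C is not in the text available here, so its exact laboratory categories were not checked. Section 9.4.0 is enough to show that laboratory abnormalities are expected.
2. **What the schedule supplies.**
   - 7.2.2 and 7.2.4: CBC, creatinine, bilirubin, ALT, glucose and lipids, within 35 days before celecoxib.
   - 7.8.0: telephone contacts, a treatment diary, celecoxib levels.
   - 7.9.0: history, physical examination, biopsies, adherence check, celecoxib level.
   - 7.10.0: 5 ml samples for celecoxib level, sent through the institution's chemistry laboratory.
   - 8.0: laboratory row marked before treatment only; drug-assay row marked before treatment and at months 2, 4 and 6.
3. **Count.** Safety panels before treatment: 1. Safety panels in months 1 to 6: 0. Drug-level draws in months 1 to 6: 3.
4. **Could the calendar be a damaged table?** This is unlikely. The prose of 7.2, 7.8, 7.9 and 7.10 agrees with it at each point.
5. **What follows.** Toxicity with symptoms or signs can surface in a telephone call or at the month 6 visit, lead to a test, and so reach the rule. Symptomless laboratory toxicity has no scheduled route, and the month 6 visit does not close the gap.

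**Scale.** The documents give no rate for laboratory toxicity. If the true rate of grade 3 or higher laboratory events were p, the chance that at least one of 40 patients has such an event is 1 − (1 − p)^40:

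- p = 1%: 1 − 0.99^40 = 0.33
- p = 3%: 1 − 0.97^40 = 0.70
- p = 5%: 1 − 0.95^40 = 0.87

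These are chances that an event occurs under assumed rates. They are not chances that it goes unseen. If half of such events were clinically evident, the chance of at least one silent event would be 1 − (1 − p/2)^40, which is 0.18, 0.45 and 0.64. The conclusion does not depend on any of these values.

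**The case against.** The strongest reply is that this is a gap and not a contradiction. Section 9.5.0 says what to do once a toxicity has been found. No section promises a scheduled test for every category, so a broad rule and a lean schedule can both be followed to the letter. That is correct, and a reader who infers that the two sections flatly contradict each other goes too far. What stands is that following both exactly leaves part of the rule's stated scope without any scheduled observation, and the protocol does not say so.

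Other strong readings are also unsupported:

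- *Every grade 3 event ends treatment.* It does not; the investigator must judge it possibly related to celecoxib.
- *There is no blood test after baseline.* Celecoxib levels are drawn three times. It is the safety panel that is not repeated.
- *Laboratory toxicity cannot trigger the rule.* An unscheduled test is not prohibited. Patients are asked about toxicity every 2 weeks, and 9.5.0 has adverse events followed according to good medical practice. That clause, however, concerns events already noticed and schedules no test.
- *The reviews would report zero laboratory toxicity.* They cover all recorded adverse events, including any found by unscheduled tests. The supportable word is under-count.

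It is also fair to say that hepatitis, jaundice and gastrointestinal bleeding in the 9.4.0 list may show themselves clinically, so only the liver function test entry bears directly on the point. Entry limits on marrow, kidney and liver values (5.1.2) exclude patients who start with marked abnormalities, but they say nothing about change on treatment.

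**Conclusion.** The point holds in a limited form. The rule reaches laboratory-defined toxicity, the schedule provides one safety panel before treatment and none after, and symptomless events can be found only by chance or by an unscheduled test. The cumulative reviews would under-count them, and a low count could not be read as evidence of safety.

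The conclusion rests on the calendar and on the agreement of 7.2, 7.8, 7.9 and 7.10 with it. It assumes that no appendix or data-collection template, none of which is in the available text, schedules these tests. The number of patients affected cannot be estimated from the documents.

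No endpoint, sample size or efficacy analysis is affected, and the separate suspension rule for cardiovascular events (9.8.0, 10.3.7) is outside this point. Reconciling the sections is a cheap improvement.

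**What to change.** Reconcile sections 7.9.0, 8.0 and 9.5.0 in one of two ways:

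- the schedule supplies the laboratory values that the rule relies on; or
- 9.5.0 and the safety reports state that laboratory-defined toxicity is not systematically assessed on treatment, and that its absence from the reports is not evidence of safety.

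Which route to take, and under the first route which tests and when, is for the clinical investigators. Nothing here proposes a test schedule or a change to the stop rule.

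The second route costs only wording. The first costs at most routine assays, and possibly an extra tube, at blood draws that already take place and already go through the institution's chemistry laboratory (7.10.0). The calendar shows no physician evaluation at months 2 or 4, so if results were produced then, the protocol would also need to say who reviews them.

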## 9.0 MANAGEMENT OF ADVERSE REACTIONS (ADRS)

### 9.1.0. Definition of Adverse Event

An adverse event is any condition that appears, worsens, or increases in frequency after starting the study drug. Investigators will attempt to define drug related versus non-drug related adverse events; however, all adverse events, whether thought to be drug related or not, will be noted in the records and reported to the IRB according to the guidelines for filing reports of adverse experiences at M. D. Anderson (Appendix B). Severe adverse events will be reported using the MDACC severe adverse event reporting form (Appendix J).

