### **7.3.0 Enrollment on the study**

The informed consent will be reviewed and discussed with subjects who are approached for enrollment on the study. A potential study candidate who is interested in enrollment can be provided with a copy of the informed consent to review at home. If after returning home, a potential study candidate expresses interest in enrolling in the study but is unable to be physically present at MD Anderson at the time of signing the informed consent due to physical distance, he or she may fax the signed consent form to a clinical study investigator and mail the original at the same time. The subject will be enrolled on the study once a clinical study investigator has signed the informed consent. In addition, before the patient starts his or her colonic procedure the patient will then be re-consented by the clinical study investigator. After signing an informed consent, each subject will complete a demographic data forms including the following information: Age, Sex, diagnosis, registration number, telephone number and address. Subjects will also complete questionnaires regarding medications, vitamins, dietary food questionnaire, and nutritional supplements (Appendix H). The original copy of the consent form will be filed in the patient's medical records. A copy of the consent will be kept in the patient's study file, and a second copy will be given to the patient. In the event that the patient has an opportunity to qualify for other research studies, the patient may sign up two different consents. Once the patient is determined non-evaluable during the initial colonic procedure (having less than 20 polyps), the patient will be enrolled on an alternative research study that require the patient to have less than 20 polyps on their initial colonoscopy.

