### **7.4.0 Celecoxib administration**

Following the initial colonoscopy procedure, subject will start celecoxib at a dose of 400 mg po bid with meals. Celecoxib treatment will be continued for 6 months.

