### **7.5.0 Sampling procedure during colonoscopies**

A study investigator with clinical privileges to perform gastrointestinal endoscopic procedures will obtain a total of 23 specimens during each endoscopic procedure before celecoxib therapy starts and after 6 months of treatment. One or two forceps biopsy specimens will be obtained from 10–20 separate polyps (the total number of colonic polyps sampled will be 20). The polyps will be sampled in a fashion that is representative of the size of the polyp population. Three additional specimens will be obtained from normal-appearing colonic mucosa. If colorectal mucosa is carpeted with polyps, indigo carmine will be used to distinguish normal from adenomatous mucosa.

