#### **9.6.0 Serious Adverse Events**

Serious Adverse Experience -Any adverse drug experience that results in any of the following outcomes:

- Death

- A life-threatening adverse drug experience - any adverse experience that places the patient, in the view of the initial reporter, at immediate risk of death from the adverse experience as it occurred. It does not include an adverse experience that, had it occurred in a more severe form, might have caused death.

- Inpatient hospitalization or prolongation of existing hospitalization
- A persistent or significant disability/incapacity - a substantial disruption of a person's ability to conduct normal life functions.
- A congenital anomaly/birth defect.

Important medical events that may not result in death, be life-threatening, or require hospitalization may be considered a serious adverse drug experience when, based upon appropriate medical judgment, they may jeopardize the patient or subject and may require medical or surgical intervention to prevent one of the outcomes listed in this definition. Examples of such medical events include allergic bronchospasm requiring intensive treatment in an emergency room or at home, blood dyscrasias or convulsions that do not result in inpatient hospitalization, or the development of drug dependency or drug abuse.

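### Biopsy complications confined to the time before the first celecoxib dose fall outside the adverse-event definition, and no routine contact looks for complications after the month-6 biopsies

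*Combined protocol and SAP*

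**What the plan says.** All references are to the combined protocol and SAP.

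- **When the AE window opens.** Section 9.1.0: "An adverse event is any condition that appears, worsens, or increases in frequency after starting the study drug". The same section records AEs whatever their suspected cause, so the restriction is one of time, not of attribution. It refers to institutional reporting guidelines in Appendix B.
- **When the biopsies are taken.** Section 7.5.0 has the endoscopist "obtain a total of 23 specimens during each endoscopic procedure before celecoxib therapy starts and after 6 months of treatment". Section 7.4.0 fixes the order: "Following the initial colonoscopy procedure, subject will start celecoxib at a dose of 400 mg po bid with meals". It gives no interval between procedure and first dose.
- **The patient's status by then.** Under section 7.3.0 the patient is enrolled once an investigator has signed the consent form, and "before the patient starts his or her colonic procedure the patient will then be re-consented by the clinical study investigator". Patients found at that colonoscopy to have too few polyps (under 20) are non-evaluable and move to another study.
- **The named risk.** Section 9.4.0, which lists expected AEs, says of the endoscopic procedures: "These potential risks can include bleeding and bowel perforation". It also says that the study biopsies should add little to the small risk of endoscopy.
- **Serious events.** Section 9.6.0 begins: "Serious Adverse Experience -Any adverse drug experience that results in any of the following outcomes". Section 9.7.0 sets a 24-hour reporting rule for serious events regardless of relation to the medication, with no start date.
- **Scheduled contact.** Section 7.8.0 places calls at 72 hours after the first dose and "every 2 weeks (+/- three days) thereafter for toxicity assessment for the entire period of the study (6 months". The calendar in section 8.0 has no toxicity evaluation before treatment and none after month 6.
- **After a procedure.** Section 9.5.0 gives at least 60 minutes of observation, contact numbers and a request to call about heavy bleeding or abdominal pain. Its only later contact is conditional: "As a part of the follow-up in case of unacceptable toxicity development, a telephone contact will be made at 30" ± 7 days after celecoxib is discontinued.

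**The concern.** The protocol names complications of its sampling procedure as expected AEs, but starts its AE clock after the first of the two procedures. A complication confined to the interval before the first dose is recognised in section 9.4.0 and excluded by section 9.1.0. After the second procedure the difficulty is different: events count, but no routine contact is scheduled to find them.

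The stake is the safety record. The six-monthly cumulative review in section 9.5.0 and the independent monitors' report in section 9.5.1 both work from recorded AEs. If some procedure complications are not AEs by definition, and others are recorded only when the patient volunteers them, the statement in section 9.4.0 that the biopsies add little risk cannot be reliably checked against the trial's own data.

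**Working it through.** The plan gives no figure to reproduce. The check sets the definition against the order of procedures and the contact schedule.

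**Step 1: classify a biopsy complication by when it arises.**

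| When it arises | Meets section 9.1.0? | Routine scheduled contact that would look for it |
|---|---|---|
| After the baseline biopsies, before the first dose, no worsening afterwards | No | None before the dose. The 72-hour call comes later, and an event mentioned there still fails the definition |
| Before the first dose, then worse or more frequent after it | Yes | 72-hour and two-weekly calls |
| First appears after the first dose | Yes | 72-hour and two-weekly calls |
| After the baseline colonoscopy in an enrolled patient who never takes celecoxib | No; the window never opens | None; calls are timed from the first dose |
| Within about an hour of the month-6 biopsies | Yes | Observation for at least 60 minutes |
| Later after the month-6 biopsies | Yes | None. The patient may call; the 30 ± 7 day call applies only after unacceptable toxicity |

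The first and fourth rows are the gap in the definition. The last row is the gap in ascertainment.

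**Step 2: does the serious-event wording close the baseline gap?** Section 9.7.0 is broad on causality and silent on timing, which favours coverage. But it acts on serious events, and section 9.6.0 defines these as drug experiences. A perforation in a patient who has not yet taken the drug is hard to place there. The reading is ambiguous: neither clearly in nor clearly out.

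**Step 3: could a routine contact follow the month-6 biopsies?** The study schema (section 4.0) and the month-6 list (section 7.9.0) both put the history for toxicity before the repeat colonoscopy. Calls end at 6 months. With the ± 3 day window the last two-weekly call might fall after the procedure, but nothing requires it. Unconditional scheduled contacts after the month-6 biopsies: 0. Conditional contacts: 1.

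**Step 4: exposure.** Inputs are 23 specimens per procedure (section 7.5.0), two procedures, and 40 patients (section 3.0).

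- Per patient: 23 × 2 = 46 specimens.
- Procedures: 40 × 2 = 80.
- Specimens: 40 × 46 = 1,840, that is 23 × 40 = 920 at each time point.

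These figures assume that 40 patients complete both procedures. Section 7.12.0 replaces drop-outs, so baseline colonoscopies may exceed 40. For patients with fewer than 20 polyps, the documents do not say whether any research specimens are taken before they leave the study.

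**Step 5: events missed.** The number missed at baseline would be (patients having the baseline procedure) × (complication risk per procedure) × (share of complications confined to the pre-dose interval). The documents give neither the risk nor the interval that determines the share, so the product cannot be computed.

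**The case against.** The case for leaving the text alone has real substance.

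- **Most timings are covered.** A reader might infer that all complications of the baseline biopsies are excluded. They are not: one that appears or worsens after the first dose is an AE, and early calls could detect it. If dosing follows the colonoscopy closely, the excluded interval is short. This limits the point to pre-dose events and to patients who never dose.
- **Month 6 is not ignored.** A reader might also infer that these complications are never enquired into or lie outside the definition. Neither is right. They follow drug start, and section 9.5.0 provides observation, telephone numbers and an explicit request to call. What stands is that detection is passive after the first hour. That is a weaker safeguard for patients living far away: section 7.13.0 plans travel for those over 300 miles from the centre with a stay of one or two nights, and they may be treated elsewhere.
- **The study may add little risk.** Section 9.4.0 expects no appreciable increase from the biopsies, and section 2.7.0 notes that these patients need repeated surveillance colonoscopies anyway. It would be unfair to say that the study creates the whole risk. But the expectation is one that the safety data should be able to test.
- **Other routes exist.** The cumulative review also covers premature terminations, and the monitors review pretherapy requirements and all toxic effects. A serious baseline complication might surface there. These routes do not make it a recorded AE.
- **Appendix B is unseen.** Institutional rules could set a wider reporting window. This is a genuine uncertainty and limits confidence in the baseline half.

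**Conclusion.** The point holds in a limited form. Sections 9.1.0 and 9.4.0 conflict for biopsy complications confined to the time before the first dose and for enrolled patients who never start the drug, and sections 9.6.0 and 9.7.0 do not clearly resolve this. Separately, no routine contact follows the month-6 biopsies.

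The design exposes every patient who has the baseline procedure to the first gap and every patient who has the month-6 procedure to the second. The 1,840 specimens measure exposure, not missed events, and it would be wrong to conclude that complications will be under-reported by any particular amount. The documents support only that under-recording is possible, to an unknown extent. The conclusion rests on reading the AE definition literally and on Appendix B not already widening the window.

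The biomarker endpoints are unaffected. So is the cardiovascular stopping rule in section 10.3.7, which counts toxicity during the 6 months on drug. This is a correction that should be made to safety definitions and data collection, not a threat to the main analysis.

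**What to change.** 1. In sections 9.1.0 and 9.6.0, start AE and serious-event collection at the baseline study colonoscopy for every enrolled patient, whether or not celecoxib is later started. Word both definitions to cover procedure-related as well as drug-related events, and reconcile them with section 9.4.0 and with Appendix B. The 24-hour rule in section 9.7.0 would then apply without ambiguity.
2. Make the 30 ± 7 day telephone contact in section 9.5.0 routine for all patients, timed from the month-6 colonoscopy, and add it to the calendar in section 8.0.
3. Ask specifically about biopsy complications at that call and at the existing 72-hour call.

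The cost is protocol wording plus one extra call per patient (about 40 calls) by staff already making the two-weekly calls. More events will be reported, some of them minor. Treatment does not change.
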